## 1 List of Abbreviations

Abbreviation	Abbreviation definition
AE's	Adverse events
BMC	Boston Medical Center
BUMC	Boston University Medical Campus
cc	Cubic centimeters
FDA	Food and Drug Administration
ID	Identification
IOP	Intraocular Pressure
IRB	Institutional Review Board
mL	Milliliters
SAEs	Serious adverse events
SOC	Standard of care
UP	Unanticipated problem
VA	Visual acuity

## 2 Protocol Summary

Title:	Glaucoma Drop Aid Study
Population:	Male and Female patients of Boston University Eye Associates, 18 or older, having been receiving the same topical medication for treatment of glaucoma for a minimum of two months
Intervention:	Control: 
 
No Glaucoma Drop Aid Device
 
 Drop Aid Devices: 
 
Simply Touch Eye Drop Applicator
 
Fabrication Autodrop Eye Drop Guide
 
Owen Mumford OP 6100 Autosqueeze
 

Objectives:	To determine the efficacy of drop aid devices for improving medication compliance, visual function, and decreasing medication waste for patients at BMC
Design/Methodology:	Arm A: No intervention- Control Arm B: Active Comparator- Eye Drop Aids  Participants will be randomly assigned into one of the study arms. If placed into Arm A, no drop aid device will be assigned. If placed into Arm B, participants will be assigned one of the three drop aid devices (Simply Touch Eye Drop Applicator, Fabrication Autodrop Eye Drop Guide, or the Owen Mumford OP 6100 Autosqueeze).
Total Study Duration:	Approximately 1 year
Subject Participation Duration:	Subject participation length is variable based on appointment wait times and availability. The minimum duration of this study is 6 weeks.

### 3 Background/Rationale & Purpose

#### 3.1 Background Information

Glaucoma is a disease characterized by an increased intraocular pressure, resulting in damage to optic nerve. This disease can be diagnosed by measuring visual field loss, identifying other changes in the physical structures of the eye and by measuring IOP. If untreated, glaucoma can result in preventable vision loss.

Glaucoma is commonly treated with prescription eye drops. It is critical that patients receive the correct dose and frequency of eye drop medication as prescribed. This will prevent disease advancement and decrease the chances of vision loss. However, patient compliance with medication limits symptom improvement due to deliberate misuse, financial concerns, or unintentional issues in drug delivery. Some patients have difficulty putting in the correct amount of eye drops themselves. Common problems are from a patient missing their eye, delivering too much medication, or they are unable to squeeze the bottle properly. This can create further problems with pharmacy refills, as well as financially from buying an increased number of prescriptions. In order to ensure patients are receiving the correct amount of drops with each use, drop aids are available at local pharmacies for purchase. These are not commonly recommended because they can be costly and their usefulness has not yet been proven. Although if a drop aid proves to be effective, they may result in a decrease of cost for the patient in the long term by allowing a decrease in premature completion of the bottle.

This study aims to determine the efficacy of glaucoma drop aids delivery of ophthalmic medications by improving medication compliance, visual function, and decreasing medication waste in the patient population at BMC.

This study will be conducted in compliance with the protocol, applicable regulatory requirements, and BMC/BU Medical Campus Human Research Protection policies and procedures.

#### 3.2 Rationale and Purpose

The ophthalmology department at Boston Medical Center sees on average 275 glaucoma patients weekly, 80 percent of which are placed on glaucoma medications. It is critical for these patients to receive the correct dose and frequency of their eye drops, in order to prevent disease advancement and decrease the chances of vision loss. However, a majority of patients are unable to properly deliver the eye drops into their eyes due to poor vision or difficulty squeezing drop bottles. Furthermore, when patients are able to instill drops into their eyes, they often deliver more than a necessary amount, leading to premature completion of the bottle. This is an issue in the United States, as most glaucoma patients are on 2 to 3 different medication drops and Medicare Part D sponsors permit refills at only 70% of predicated days of use, accounting for about half of glaucoma patient population. Self-reported studies also showed that approximately 25% of patients reported problems with early exhaustion of eye drop bottles. The average size of a glaucoma medication bottle is around 10 cc and these medications, when used 2 to 3 times daily, are expected to last patients an entire month. When used in excess or reduction, problems may occur with pharmacy refills, an addition to financial burdens from buying an increased number of prescription refills. In the absence of good medication compliance and response, patients often have to undergo costly surgical procedures that can place them at an increased risk of infection and loss of vision, while still requiring postoperative management with ophthalmic drops, in addition to being closely monitored by eye care providers.

In order to ensure patients are receiving the correct amount of drops with each use, there are many drop aid assistive devices available for purchase on the market; however, these drop aids are not routinely offered to our patients because of their unproven cost benefit ratio, and the poorly studied efficacy of the devices. Although, if a drop aid proves to be effective, the cost of the drop aid devices would more than pay themselves through the improvement in medication compliance and visual function of our patients. The “Glaucoma Drop Aid Study” aims to determine if using drop aids during the administration of eye drop medication leads to better results for patients with glaucoma at Boston Medical Center. The implications of this study may show an improved delivery system of ophthalmic medications thus improving medication compliance, visual function, and even decreasing medication waste.

## 4 Objectives

### 4.1 Study Objectives

The primary objective of this study is to compare efficiency of various drop aids for glaucoma medications objectively via changes in intraocular pressure. The different drop aids that are utilized are the Simply Touch Eye Drop Applicator, the Fabrication Autodrop Eye Drop Guide, and the Owen Mumford OP 6100 Autosqueeze. The central hypothesis is that the use of a drop aid device increases efficiency of glaucoma medication when comparing changes in intraocular pressure.

A secondary objective of this study is to evaluate how often a patient missed their eye when instilling drops with various drop aids in order to assess whether drop aids can decrease medication waste, increase medication compliance, and improve visual function. Additionally, the study will analyze how satisfied the patient is with their drop aid and the likelihood they would continue to use one outside of the study. These satisfaction means will be evaluated with a patient satisfaction survey approximately 3 weeks and 6 weeks after enrollment.

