#### 4.2.1 Primary Outcome Measures

The objective of this study is to compare efficiency of various drop aids for glaucoma medications objectively via changes in intraocular pressure.

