### 5 Study Design

This interventional clinical trial is a prospective, single center, randomized controlled study. Patients being treated for their glaucoma at BMC's Yawkey Eye Clinic will be selected. Patients will be randomly placed, without manipulations by the principle investigator or any member of the research team, on one of the drop aid devices (including Fabrication Autodrop Eye Drop Guide, Simply Touch Eye Drop Applicator, Owen Mumford OP 6100 Autosqueeze), in addition to a no drop aid control, for a total of 4 groups.

Subjects have an equal chance of being randomized to one of the following study arms:

- Arm A: No intervention – Control
- Arm B: Active Comparator- Eye Drop Aids Including:
  - Simply Touch Eye Drop Applicator
  - Fabrication Autodrop Eye Drop Guide
  - Owen Mumford OP 6100 Autosqueeze

The primary endpoint is the comparison of baseline IOP measurement and follow-up IOP measurement. This comparison will determine the efficacy of using a drop aid. The secondary endpoints include the precision of the drop aid, patient satisfaction, and their likelihood to use a drop aid outside of the study. Data collection for assessment of study objectives will be obtained via standard of care clinic visits and completion of study diary and satisfaction survey by the patient with assistance of research team, if needed.

See the Appendix section 15.1 for a schematic of the study design and section 15.3 for drop aid labels and instructions.

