## 12 Statistical Plan

### 12.1 Study Hypotheses

#### 12.1.1. Primary Objective: Intraocular Pressure

Formal hypothesis: Drop aids will be cost-effective in delivery of ophthalmic medications by improving baseline IOP measures to six week visit.

Testable hypothesis: Patient baseline IOP measures will be a statistically significant improvement in accordance to the usage of a drop aid device.

Null hypothesis: The patients, who are assigned to a drop aid device baseline IOP measures will not have a statistically significant change with the usage of a drop aid device when compared to patients not assigned to a drop aid device.

Alternate hypothesis: Patients not assigned to a drop aid device will result in larger significant change when compared to patients who are assigned to a drop aid device.

$$H_0: \mu_0 < \mu_d - \delta$$

$$H_A: \mu_0 \geq \mu_d - \delta$$

Where  $\mu_0$ , is the true mean IOP change from baseline to the six week visit without the drop aid device,  $\mu_d$  is the true mean IOP change from baseline to the six week visit with the drop aid device.

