## 12.2 Sample Size Determination

The sample size was determined by the maximum number of subjects which could be randomized given the budgetary constraints of the grant funding. It was determined that a total of ten patients per group was financially feasible, thus a total of 40 patients will be enrolled in this study in approximately 1 year.

Enrolling the projected 40 subjects in 1 year is feasible, as the ophthalmology department sees approximately 275 glaucoma patients weekly. Due to the high volume of the glaucoma clinic, the study team should be able to easily recruit their target. Additionally, the study team is comprised of multiple

investigators and research assistants who have been delegated tasks on this protocol which can provide full-time recruitment coverage.

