### 12.3 Statistical Methods

A variety of statistical analysis will be used to analyze the results. A paired t-test will be the primary method of analysis. Any significant differences measured will be between the pre and post intervention, with the patient serving as their own control. However, the analysis will not be limited to a paired t-test and will also likely include ANOVA, chi-squared, p-value, linear regression, among others. Other outcomes such as length of time until completion of drops will also be measured and compared to no drop aid controls. Significant differences will be measured with similar statistical analysis as stated previously. Satisfaction of use will be measured with a survey and results will be averaged among those in the same cohort. Any significant differences will also be measured with similar statistical analysis stated previously.

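### The primary objective compares devices, the primary hypothesis pools them, and the named primary test is pre/post within patient: no single primary IOP contrast or error control is set

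*Combined protocol and SAP*

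**What the plan says.** Three parts of the plan each define the primary question on intraocular pressure (IOP).

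- **Objective.** Section 4.1 sets a comparison of the various drop aids as primary and lists the three devices: "The primary objective of this study is to compare efficiency of various drop aids for glaucoma medications objectively via changes in intraocular pressure". Section 4.2.1 gives the primary outcome in the same terms, with no contrast named: "The objective of this study is to compare efficiency of various drop aids for glaucoma medications objectively via changes in intraocular pressure".
- **Hypothesis.** Section 4.1 goes on: "The central hypothesis is that the use of a drop aid device increases efficiency of glaucoma medication when comparing changes in intraocular pressure". Section 12.1.1 formalises this with two means only. The control mean is mu_0, and mu_d "is the true mean IOP change from baseline to the six week visit with the drop aid device". No hypothesis in 12.1.1 to 12.1.4 compares one device with another, or a single device with control.
- **Method.** Section 12.3 names a paired t-test as the primary method, with differences taken pre to post and each patient as his or her own control. It then says that "the analysis will not be limited to a paired t-test and will also likely include ANOVA, chi-squared, p-value, linear regression, among others". It gives no grouping, testing order, alpha or multiplicity rule.

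On design, section 5 allocates patients to one of three devices, "in addition to a no drop aid control, for a total of 4 groups". Section 12.2 gives the size: "It was determined that a total of ten patients per group was financially feasible, thus a total of 40 patients will be enrolled".

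**The concern.** A reader cannot tell which comparison decides the trial. The objective points to differences among devices, the hypothesis to any device against none, and the primary method to change within patients. The last of these makes no use of the randomised control group.

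With the contrast unset and the list of tests open, IOP could be analysed within arm, pooled, device against control, device against device, or by ANOVA. If a statement about a particular device were taken from whichever of these reached significance, its error rate would exceed the level of a single test. Each such comparison would also rest on ten patients per group.

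**Working it through.** **Inputs**
- Groups: 4, three devices and control (section 5).
- Size: 10 per group (section 12.2). Check: 4 x 10 = 40, the stated total. No more of the sample size can be rebuilt, because the plan gives no alpha, power, effect or SD.
- Allocation: taken as 1:1:1:1 from ten per group. The equal-chance sentence in section 5 lists Arm A and Arm B and could also be read as 1:1, so it should be reconciled with 12.2.
- Alpha: not stated. Assumed two-sided 0.05 per test.
- Data: normal IOP change, equal variance, no dropout (assumed).

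**Number of contrasts.** Device versus control: 3. Device versus device: 3. All pairs: 4 x 3 / 2 = 6.

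**Chance of at least one false positive when no group differs.** For k independent tests it is 1 - 0.95^k. Within-arm tests are independent, so the formula applies to them. Between-arm tests share groups, so those were simulated (200,000 null trials; 40,000 for the pooled contrast).

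| IOP tests at 0.05 each | Formula | Simulated |
|---|---|---|
| Pooled devices vs control, 30 vs 10, one test | 5% | 5.0% |
| Three device vs control | - | 12.5% |
| Three device vs device | - | 12.3% |
| All six pairs | - | 20.4% (19.7% with pooled SD) |
| Paired t-test in three device arms | 1 - 0.95^3 = 14.3% | 14.1% |
| Paired t-test in all four arms | 1 - 0.95^4 = 18.5% | 18.4% |

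**Would ANOVA protect the pairwise tests?** If a significant ANOVA were required first, the error would be 4.9% when all four groups are equal. It would be 12.0% when control differs and the three devices are equal. The plan specifies no such step.

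**Does the named primary test answer either question?** A paired t-test responds to any change shared by all arms. Suppose every arm, control included, drifts by the same amount and no device has an effect. The chance that at least one device arm is significant is then:

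| Common drift (SD of change, assumed) | 0 | 0.25 | 0.5 | 0.75 | 1.0 |
|---|---|---|---|---|---|
| At least one of three device arms | 14.1% | 29.4% | 64.9% | 91.7% | 99.3% |

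The documents give no drift figure, so this is a range and not a forecast.

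**What each choice can detect** (80% power, two-sided, noncentral t). Pooled 30 vs 10 at 0.05: 1.05 SD. One device vs control, 10 vs 10, unadjusted: 1.32 SD. With Bonferroni: 1.57 SD for three tests (family error 4.4%) and 1.73 SD for six (4.1%).

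**Cost of Dunnett adjustment.** The critical value for three comparisons with control on 40 - 4 = 36 df is 2.453, against 2.028 unadjusted. The ratio is 2.453 / 2.028 = 1.21, so intervals are about 21% wider.

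**The case against.** The case for the plan has four parts.

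1. *A primary method is named.* Section 12.3 does name one and ties significant differences to the pre/post change. Its later mention of significant differences concerns satisfaction, and chi-squared suits the survey items rather than mean IOP. This stands: a reader who infers that 12.3 permits any test on any grouping, with nothing primary, goes further than the text. But the named test matches neither the device-comparison objective nor mu_d against mu_0.

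2. *The pooled question is stated repeatedly.* It appears in the two-arm description in section 2, the rationale in 3.2, the central hypothesis in 4.1, section 5 and 12.1.1. This also stands, and it is the reason to make the pooled contrast primary. It does not remove the conflict with the objective and the primary outcome.

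3. *No device claim is promised.* Nowhere does the plan commit to naming a best device or to declaring one effective. This stands, so the inflated error is conditional on such claims being made.

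4. *This is a small, minimal-risk study sized by budget.* True, and it bears on severity. But the protocol does not call itself a pilot. It states formal hypotheses, and section 5 says the IOP comparison will determine efficacy.

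**Conclusion.** The mismatch is in the current text: objective, hypothesis and primary method define three different comparisons, and no contrast or error control settles which one counts. This should be fixed before analysis.

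The size is conditional. At an assumed two-sided 5% per test with 4 groups of 10, unadjusted device-specific testing carries a false-positive chance of about 12.5% (three device-versus-control tests) to 20% (six pairs), with 18% for four within-arm tests. The single pooled contrast stays at 5%.

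Three stronger readings are not supported.
- That the trial's claims will rest on error far above 5%. No device claim is committed to, and the plan states no alpha to exceed.
- That a false positive is likely. Even with three device within-arm tests, six pairs, the pooled contrast and ANOVA all open (11 tests), the figure is about 26%, and the plan does not specify that set.
- That 12.1.1 already implies a two-sided 5% test. Its inequalities are one-sided, with a delta that has no value and no stated level.

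**What to change.** - **Sections 4.1, 4.2.1, 12.1.1 and 12.3:** name one primary contrast, Arm B (three devices pooled) versus Arm A on IOP change from baseline to the six-week visit. State its alpha and sidedness.
- **Section 12.1.1:** restate the null and alternative to match. Define delta or remove it, and make the direction of the inequalities agree with the prose.
- **Section 12.3:** replace the sentence that makes the paired t-test primary with a between-arm test, for example a linear model of follow-up IOP on arm and baseline IOP. Remove the open end of the list of tests.
- **Secondary:** three device-versus-control contrasts with Dunnett adjustment.
- **Device versus device:** estimates with 95% confidence intervals and no claim of a best device.
- **All other IOP analyses,** including pre/post tests: labelled exploratory.

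The cost is wording, with no extra patients, visits or data. Device-versus-control intervals become about 21% wider.

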### 4.2 Study Outcome Measures

The efficiency of various drop aids will be measured through the subject’s glaucoma progression at the end of the study. On the day of enrollment, the subject’s IOP and visual acuity will be measured as part of their standard of care exam. This information is recorded as the baseline exam, and will be compared to measure the patient’s glaucoma progression at the end of the study. Subjects will be required to record the date on which they began each of their glaucoma eye drop bottles, and the date each bottle was finished in a study diary provided by the research team. Subject’s satisfaction will be measured through a brief satisfaction survey approximately 3 weeks after their enrollment. After at least 6 weeks of study participation, subject will be followed up with their regularly scheduled glaucoma provider where they will fill out a second brief satisfaction survey. The study diary will be collected and a routine eye exam will be conducted, with their IOP checked as part of a standard of care clinic visit.

All surveys were created by a member of the research team. The satisfaction survey includes five questions to assess the precision of the drop aid device, overall patient satisfaction, and willingness to use the device long term. The questions are multiple choice questions in which the patient circles the answer that best reflects their response.

Reference Section 12.0 for further statistical analysis explanations.

#### 4.2.1 Primary Outcome Measures

The objective of this study is to compare efficiency of various drop aids for glaucoma medications objectively via changes in intraocular pressure.

#### 4.2.2 Secondary Outcome Measures

The following secondary outcomes will also be measured:

1. Number of times a patient missed their eye when instilling eye drops
2. Patient satisfaction responses with treatment arms
3. Intention to use a drop aid long term

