#### 12.1.2. Secondary Objective: Drops Missed

Formal hypothesis: Drop aids will be effective in delivering the proper amount of drops, thereby reducing the number of missed drops for patients.

Testable hypothesis: Differences in drops missed with drop aid device compared to without drop aid device will show efficacy in drop aid device.

Null hypothesis: Patients assigned to a drop aid device will not result in less drops missed when compared to patients who are not assigned to a drop aid device.

Alternate hypothesis: Patients assigned to a drop aid device will result in minimal missed drops when compared to patients who are not assigned to a drop aid device.

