15.2.4 Satisfaction Survey

**Study ID:** \_\_\_\_\_

**Name of study team member completing this form:** \_\_\_\_\_

**Date:** \_\_\_\_\_

**Study Visit:**     3-week phone call         Follow-up clinic visit

1. Do you like the drop aid?
  - a. Yes
  - b. No
  - c. I am not on a drop aid
  - d. I did not use the drop aid
2. Is it easier to instill drops with the help of the drop aid compared without the drop aid?
  - a. Yes
  - b. No
  - c. I am not on a drop aid
  - d. I did not use the drop aid
3. How many times did you miss instilling drops with the help of drop aid?
  - a. None
  - b. 1
  - c. 2
  - d. 3 or more
  - e. I am not on a drop aid
  - f. I did not use the drop aid
4. How many times do you miss instilling drops just using your glaucoma drops?
  - a. None
  - b. 1
  - c. 2
  - d. 3 or more
5. Would you use the drop aid long term?
  - a. Yes
  - b. No
  - c. I am not on a drop aid
  - d. I did not use the drop aid

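### Missed drops is a number of misses with no denominator of drops attempted, so it does not measure the precision of the drop aid and can be biased by a change in compliance

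*Combined protocol and SAP*

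**What the plan says.** Section 4.2.2 lists the outcome as "Number of times a patient missed their eye when instilling eye drops". Section 12.1.2 tests it between groups. Its null hypothesis is "Patients assigned to a drop aid device will not result in less drops missed", set against patients without a device, and it uses no rate or proportion. Section 4.1 gives its purpose: misses are evaluated "in order to assess whether drop aids can decrease medication waste, increase medication compliance, and improve visual function". Sections 4.2 and 5 call the construct the precision of the drop aid.

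The only instrument is the survey in Section 15.2.4. Its third item asks "How many times did you miss instilling drops with the help of drop aid" and its fourth asks "How many times do you miss instilling drops just using your glaucoma drops". The numerical answers to both are none, one, two, or three or more. Neither item has a recall period, and no item asks how many drops were attempted.

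The diary does not fill the gap. Section 4.2 states the requirement as "Subjects will be required to record the date on which they began each of their glaucoma eye drop bottles, and the date each bottle was" (the sentence goes on to the emptying of the bottle), so it yields bottle dates and not instillations. Section 12.3 names no rate, offset or regimen adjustment. Sections 7.1 and 7.2 do not restrict the number of drugs, the dosing frequency or the number of treated eyes.

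**The concern.** Precision is misses per attempt. The plan records misses alone, so two separate quantities are mixed: how often a drop misses, and how many drops were tried.

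Attempts vary for two reasons with different consequences. Regimen (drugs, doses per day, treated eyes) is fixed before randomisation, so it inflates the spread within groups. Doses actually taken can change after randomisation because of the device, and randomisation cannot balance that. Section 4.1 uses this outcome to judge whether aids raise compliance, yet higher compliance means more attempts and, at equal precision, more misses. The count therefore leans against a device that gets patients to take more of their doses and towards one that leads them to skip doses.

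**Working it through.** **Plan's own figures.** Section 12.2 gives 10 per group × 4 groups = 40, set by budget, which reproduces. No effect size, SD or power is stated for missed drops, so there is no further figure to reproduce.

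**Inputs from the documents.** Section 3.2: "most glaucoma patients are on 2 to 3 different medication drops", used 2 to 3 times daily (read here as the frequency of each drug). Follow-up is at least 6 weeks, or 42 days. The survey scale stops at three or more. **Assumed:** miss probabilities of 1% and 5%, all compliance levels, and a recall period covering the whole 42 days in step 1.

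**1. Regimen.** Expected misses = attempts × miss probability.
- Attempts per treated eye: 2 × 2 = 4 a day to 3 × 3 = 9 a day. Over 42 days: 168 and 378. Ratio 9/4 = 2.25.
- The survey answer is treated as binomial, with three or more scored as 3:

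| Miss probability | Attempts | True mean | Share answering three or more | Mean on survey scale |
|---|---|---|---|---|
| 1% | 168 | 1.68 | 24% | 1.55 |
| 1% | 378 | 3.78 | 73% | 2.60 |
| 5% | 168 | 8.4 | 99% | 2.99 |
| 5% | 378 | 18.9 | about 100% | 3.00 |

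At 1% the cap shrinks the ratio to 2.60/1.55 = 1.7. At 5% almost everyone is at the ceiling and the difference vanishes.

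**2. Chance imbalance.** If attempts per day are an equal mix of 4, 6, 6 and 9, the mean is 6.25 and the SD 1.79. The standard error of the difference in mean attempts is 1.79 × √(1/10 + 1/10) = 0.80, or 13% of the mean, for one device group against control. For all devices against control it is 1.79 × √(1/10 + 1/30) = 0.65, or 10%.

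**3. Compliance.** At unchanged precision, misses are multiplied by new compliance / old compliance. The break-even cut in the per-drop miss rate is 1 − old/new.

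| Compliance (assumed) | Misses multiplied by | Break-even cut |
|---|---|---|
| 80% to 90% | 1.125 | 11% |
| 70% to 90% | 1.29 | 22% |
| 50% to 90% | 1.80 | 44% |

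For 4 drops a day over 42 days at 1%, compliance of 70% and 90% gives about 118 and 151 attempts. Expected misses go from 1.18 to 1.51 at unchanged precision (1.14 to 1.42 on the survey scale). If the device halves the miss rate, they fall from 1.18 to 0.76.

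**4. Candidate outcomes compared by simulation.** Set-up: 10 controls against 30 device patients, mean miss probability 5% in controls, gamma-distributed between patients with CV 0.5, a 7-day window, no cap, perfect recall, Mann-Whitney test. Repeated runs differ by a few points.
- Miss rate halved, attempts equal: power about 45% for the 7-day count, 52% for the 7-day rate, and 19% for an item on the last 10 drops.
- Miss rate halved and compliance rising from 70% to 90%: about 22%, 45% and 21%.
- No precision effect, compliance rising from 70% to 90%: significant results against the device in about 9% of runs for the count, 11% for misses divided by prescribed doses, and 3% for misses divided by drops actually attempted. The nominal figure is 5%/2 = 2.5%.

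**The case against.** The strongest case on the other side is that regimen is balanced by randomisation, that the missing recall period and the cap are larger faults, and that this is a secondary outcome in a trial sized by budget. Much of this stands. Regimen differences are noise and chance imbalance, not bias between groups. At a miss rate near 5% over six weeks, the ceiling does more damage than the missing denominator. No stated power depends on this outcome. But a recall period and an uncapped answer would not remove the compliance effect, because attempts within any fixed period can still differ between groups.

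It can also be said that device patients answer both survey items, and that Section 12.3 uses each patient as their own control, so regimen largely cancels. That helps only within device patients, and the time frame of the fourth item is unclear. The hypothesis in Section 12.1.2 compares patients with a device to patients without one.

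A reader might infer more than the documents support:
- That a device which improves compliance necessarily scores worse. This holds only when its precision gain is below break-even. With the miss rate halved it still scores better, and the documents give no compliance level or expected gain.
- That equally precise patients differ 4.5-fold or 9-fold. These figures need added assumptions: one patient treating one eye and another both (18/4 = 4.5), or a single drug once daily against nine drops a day (9/1 = 9). Section 3.2 alone supports 2.25-fold, and the recorded variable is a capped category and not an open count.

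**Conclusion.** The concern holds in a limited form. No denominator is defined or collected, so the outcome does not measure the precision that the plan says it should. The 2.25-fold spread between equally precise patients rests on the regimens in Section 3.2 and mainly costs power. The possible bias rests on an assumed compliance change: a 29% rise in misses for 70% to 90%, and a break-even cut of 22% (11% to 44% over the range examined). The simulated figures further assume a 5% miss probability, a 7-day window and error-free recall. The primary outcome and the stated sample size are unaffected. As this is the first-listed secondary outcome, with its own hypothesis, and the repair is cheap, the change should be made.

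**What to change.** In Sections 4.2.2 and 12.1.2, define the outcome as missed drops divided by drops actually attempted over a fixed recent window, for example the last 7 days. Reword the survey item so that every patient in all four groups gives both numbers, uncapped, for that window. In Section 12.3, compare groups on that proportion, or on the count with log(drops actually attempted) as an offset.

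Do not use prescribed doses as the denominator. They do not change when compliance changes, so the bias stays. An item on the last 10 drops removes the bias but costs much power when misses are rare (about 19% against 52% in the simulation), so it should not be the lead option.

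Cost: one reworded survey item, one extra recalled number per survey with recall error in both numbers, and a sentence in each of the three sections. No extra visits or patients are needed.
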